6.2.7 Dual Energy X-ray Absorptiometry (DXA)

DXA is the technique most commonly used to assess bone density in adults. The lumbar spine and proximal femur are recommended sites. The technique uses very low-dose x-ray exposures (<4 μ Sv per scan) and measurements are rapid.

Chapter 7. Statistical Considerations

7.1 Study design

The proposed research project involves primary and several secondary objectives. To address these aims, we will conduct a double-blind, randomized, placebo-controlled trial. 6MWT, SF-36, emPHasis-10, actigraphy and blood sampling will be performed at baseline, 3 months, 6 months and 12 months. Echocardiography will be performed at baseline, 6 months, and 12 months. DXA scan will be performed at baseline and 12 months.

7.2 Disposition of subjects and baseline comparisons

Summaries of all subjects screened, recruited, and randomized and the number who complete visits at 3 months, 6 months and 12 months post-randomization will be provided, according to the CONSORT guidelines. The treatment groups will be compared at baseline with respect to demographics and baseline measurements related to efficacy and safety without formal statistical testing.

7.3 Statistical procedures

7.3.1 Data analysis

The intent-to-treat analysis will include all randomized subjects. Hypothesis testing will use two-sided $\alpha = 0.05$ without correction for multiplicity.

7.3.2 Univariate analysis

We will characterize subjects with regard to baseline and follow-up 6MWD and other endpoints. We will summarize demographics and other predictors of clinical status. Continuous variables will be summarized by the mean, median, standard deviation, and range, as appropriate. We will use contingency tables for discrete and dichotomous variables.

7.3.3 Analyses of treatment assignment and outcome measures

The primary analysis of the primary end point will compare the absolute change in 6MWD from baseline with adjustment for baseline 6MWD and sex in linear regression models.

7.3.4 Other analyses

We will also consider longitudinal models of change from baseline over the time of the trial. Exploratory multivariate analyses will be performed incorporating all of the available endpoint assessments (baseline, 3 months, 6 months, and 12 months) in an ANCOVA model with active treatment/placebo status as the independent variable.

TTCW will be analyzed using survival analysis, stratified by assignment to AN or placebo.

7.3.5 Missing data and dropouts

We will attempt to minimize missing data, however we have planned for its occurrence. For subjects lost to follow-up, we will use all of the information available until the end of follow-up.

If a subject wishes to drop-out from the treatment phase of the study or has a serious adverse event (SAE) (whether related to study drugs or not), we will continue to follow-up with the subject for study assessments to assist with safety monitoring and to avoid the problems introduced by missing data. That is, if a subject decides that he/she does not wish to continue taking the study drug(s), the subject will stop the investigational treatment, but will still be strongly encouraged to continue to follow-up with the study personnel for all scheduled study procedures (e.g., 6MWT, phlebotomy, echocardiography, etc.), so that missing data (and assumptions regarding these data) will be minimized. The inclusion of such follow-up data will allow for analysis by intention-to-treat.

7.4 Sample size and power calculations

We will recruit a total of 84 patients with PAH with 1:1 randomization to either AN or placebo stratified by sex. We have assumed a 10% loss to follow up rate at 6 months and $\alpha = 0.05$ (2-sided) for each end point.

For our primary outcome of the difference in change in the 6MWD from baseline to six months, we have adequate power to detect an average difference of 22 meters between AN and placebo. We also have sufficient power to detect a difference of 31 meters for men and women.

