- Difference in changes in bone mineral density between AN and placebo groups at twelve months.
- Difference in side effects between AN and placebo groups at twelve months.

STUDY OBSERVATIONS:

- Subjects will be evaluated in person at screening, baseline, 3 months, 6 months and 12 months.
- Subjects will have telephone follow-up at 9 months and 54 weeks.
- Laboratory tests including a complete blood count, routine chemistry tests (creatinine and electrolytes), liver function tests, coagulation studies, calcium, and FSH will be performed at screening or baseline (if necessary).
- NT-proBNP levels and other biomarkers will be assessed at baseline, 3 months, 6 months and 12 months.

- Subjects will have six minute walk testing at baseline, 3 months, 6 months and 12 months.
- Subjects will have a transthoracic echocardiogram at baseline, 6 months, and 12 months.
- Actigraphy-measured physical activity will be collected at baseline, 3 months, 6 months and 12 months.

SAMPLE SIZE AND POWER:

A total of 84 subjects will be enrolled with 1:1 randomization to either AN or placebo. For the primary study endpoint of 6MWD, we will have 80% power to detect an average difference of 22 m from baseline to six months between AN and placebo groups ($\alpha = 0.05$).

DATA ANALYSIS:

The primary study endpoint will be evaluated using a linear regression model, adjusting for sex and baseline 6MWD. Secondary endpoints will be evaluated using linear mixed models and Cox proportional hazard models. All univariate analyses will be evaluated using t-tests or rank-sum tests and χ^2 and Fisher's exact tests as appropriate.

Brief Table of Contents

ABSTRACT.....	9
CHAPTER 1: Background and Significance.....	10
CHAPTER 2: Objectives and Specific Aims.....	12
CHAPTER 3: Screening, Subject Selection and Randomization.....	13
CHAPTER 4: Treatments.....	15
CHAPTER 5: Data Collection.....	18
CHAPTER 6: Assessment of Efficacy and Outcome Measures.....	30
CHAPTER 7: Statistical Considerations.....	34
CHAPTER 8: Quality Control.....	37
CHAPTER 9: Participant Safety and Confidentiality.....	38
REFERENCES.....	51

Contents

ABSTRACT	9
Chapter 1. Background and Significance	10
1.1 Definition and characterization of PAH	10
1.2 Traditional and novel concepts in hormonal effects on the vasculature	10
1.3 Aromatase inhibitors for use in PAH	10
1.4 Summary	11
Chapter 2. Objectives and Specific Aims	12
2.1 Objectives	12
2.2 Specific Aims	12

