From the earliest modern description, PAH has been recognized as a “female” disease. Female sex is the strongest risk factor for idiopathic and heritable PAH. Connective tissue disease-associated PAH almost always occurs in women, and female sex is associated with a significantly increased risk of portopulmonary hypertension in patients with cirrhosis. Despite the decades-old recognition of this sex predilection, surprisingly few human and experimental studies have focused on the mechanism of female sex in causing PAH and the use of treatment targeting sex hormones. While estrogen has traditionally been considered to protect from cardiovascular disease, the strong female sex predominance in PAH implicates estrogen or other sex hormones in the pathophysiology of the disease.

Aromatase converts androgens to estradiol (E2) in the periphery and is responsible for most of the E2 production in post-menopausal women and men. Our research group and others have performed several studies which suggest that aromatase and estrogen production may play an important role in the risk of PAH. Surprisingly, aromatase is present in the diseased small muscular pulmonary arteries of both experimental models and patients with PAH; anastrozole (AN) (an aromatase inhibitor) reversed pulmonary hypertension in these animal models. Finally, we have performed a small “proof of concept” randomized clinical trial which showed that AN significantly increased the six minute walk distance at three months (RCT NCT01545336). AN is a generic drug which has been FDA-approved for breast cancer for 20 years and has an excellent safety profile.

We propose a Phase II randomized, double-blind, placebo-controlled trial of AN in 84 post-menopausal women and men with PAH to determine whether AN may be an effective treatment for PAH.

Chapter 1. Background and Significance

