3.1 Recruitment

3.1.1 Identification and screening process

Subjects will be identified by the medical staff who care for patients with PAH at University of Pennsylvania, Johns Hopkins University, Vanderbilt University, Stanford University, Washington University, Rhode Island Hospital/Brown University, and University of Colorado. We expect to pre-screen approximately 950 subjects over three years between the seven centers. Potentially eligible subjects will be pre-screened and informed about that study to determine if they have an interest in enrolling. After the initial pre-screening, the subject will provide informed consent before any study procedures are performed.

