3.2 Subject selection criteria

3.2.1 Inclusion criteria

- Previous documentation of mean pulmonary artery pressure > 25 mm Hg with a pulmonary capillary wedge pressure (or left ventricular end-diastolic pressure) < 16 mm Hg and PVR > 3 WU at any time before study entry.
- Diagnosis of PAH which is idiopathic, heritable, drug- or toxin-induced or associated with connective tissue disease, congenital heart disease, portal hypertension, or HIV and receiving treatment for PAH.
- Most recent pulmonary function tests with FEV1/FVC $> 50\%$ AND either a) total lung capacity $> 70\%$ predicted or b) total lung capacity between 60% and 70% predicted with no more than mild interstitial lung disease on computerized tomography scan of the chest.
- Ability to perform six minute walk testing without significant limitations in musculoskeletal function or coordination.
- If female, post-menopausal state, defined as: 1) > 50 years old and a) have not menstruated during the preceding 12 months or b) have follicle-stimulating hormone levels (> 40 IU/L) **or** 2) < 50 years and follicle-stimulating hormone levels (> 40 IU/L), **or** 3) a bilateral oophorectomy.
- Informed consent.

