3.2.2 Exclusion criteria

- Current treatment with estrogen, hormone therapy, or anti-hormone therapy (tamoxifen, fulvestrant, etc.)
- WHO Class IV functional status.
- History of invasive breast cancer.
- Clinically significant untreated sleep apnea.
- Left-sided valvular disease (more than moderate mitral valve stenosis or insufficiency or aortic stenosis or insufficiency), pulmonary artery or valve

stenosis, or ejection fraction < 45% on most recent echocardiography (within 1 year).

- Initiation of PAH therapy (prostacyclin analogues, endothelin-1 receptor antagonists, phosphodiesterase-5 inhibitors, riociguat, selexipag) within three months of enrollment; the dose must be stable for at least three months prior to Baseline Visit. PAH therapy which is stopped and then restarted or has dose changes which are not related to initiation and uptitration will be allowed within 3 months prior to the Baseline Visit.
- Hospitalized or acutely ill.
- Renal failure (creatinine \geq 2.0).
- Hypercalcemia (\geq Grade 2 per NCI-CTCAE v4.0).
- Severe osteoporosis:
 - T score -2.5 to -3.4 without bone modifying treatment OR T score = -3.5 or lower
- Child-Pugh Class C cirrhosis.
- Current or recent (< 3 months) chronic heavy alcohol consumption.
- Enrollment in a clinical trial or concurrent use of another investigational drug (non FDA approved) or device therapy within 30 days of screening visit.
- Age < 18.

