3.3 Randomization

The Research Pharmacy at the University of Pennsylvania will prepare numbered drug kits containing 6 month supplies of AN or placebo and these will be used sequentially. Randomization will be blocked and stratified by sex. Randomization will be 1:1 AN:placebo.

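### Does the 31 m detectable difference for men and women need a stated sex split?

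*Combined protocol and SAP*

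**What the plan says.** The Protocol Summary, under Sample Size and Power, says that with 84 subjects randomized 1:1 "we will have 80% power to detect an average difference of 22 m from baseline to six months". Section 7.4 repeats the 22 m, calling the power adequate, and assumes 10% loss to follow-up at six months and a two-sided α of 0.05. It then adds: "We also have sufficient power to detect a difference of 31 meters for men and women". No SD is given, no sex split, and no power level for the 31 m beyond the word sufficient.

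Section 3.3 says: "Randomization will be blocked and stratified by sex". Section 3.1 (recruitment) and section 3.2 (eligibility) set no target or cap by sex.

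Two places bear on the likely mix. The Abstract says that "the strong female sex predominance in PAH implicates estrogen or other sex hormones in the pathophysiology of the disease", without giving a ratio. Section 3.2.1 admits women only under a condition: "If female, post-menopausal state, defined as".

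In the analysis, sex appears as a covariate in the primary regression (section 7.3.3). Sections 7.3.1 to 7.3.4 describe no analysis within sex and no interaction test.

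**The concern.** One detectable difference is given for both sexes, with no condition attached. The detectable difference within a subgroup depends on its size, so a single figure can serve both sexes only if they are about equally represented. Stratified randomization balances the arms within each sex but does not settle how many men or women enrol. The disease is described as predominantly female, so a reader may doubt that half the subjects will be men.

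If the split were clearly unequal, the claim would be too favourable for the smaller sex. A null result in that sex could then be read as more informative than it is. The trial's rationale is sex-hormone biology, and section 2.2 lists planning the Phase III sample size among its other aims, so the point is not idle.

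**Working it through.** **Inputs.**
- 84 subjects randomized 1:1, 10% loss, two-sided α = 0.05 (section 7.4). Evaluable: 84 × 0.9 = 75.6, or 37.8 per arm.
- 22 m overall at 80% power (Protocol Summary).
- 31 m for men and women (section 7.4).
- Assumed, because the documents do not say: 80% power also for the 31 m, and a common SD and equal loss to follow-up in both sexes.

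**The overall figure.** Solving 22 = (1.960 + 0.842) × SD × √(2/37.8) gives SD = 34.1 m (normal approximation), or 33.7 m with the noncentral t. The SD is not needed for the normal-approximation results below, because it cancels.

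**The 31 m.** For a sex with share f of the sample, the detectable difference is 22/√f. At f = 0.5 this is 22 × √2 = 31.1 m, which reproduces the stated figure. With the noncentral t it is 31.6 m.

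**The split it implies.** (22/31)² = 0.504. For rounding, take the most favourable case: a true overall figure of 21.5 m and a within-sex figure of up to 31.5 m. The smallest admissible share is then (21.5/31.5)² = 0.466. Since this must hold for each sex, the range is 46.6% to 53.4% men. As a check, at 54% men the women need at least 21.5/√0.46 = 31.7 m, which rounds to 32.

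**Other splits.** Power for 31 m in the smaller sex is Φ(2.802 × (31/22) × √f − 1.960). The splits are illustrative; the documents give none.

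| Split, smaller:larger | Detectable difference, smaller / larger (normal) | Same, noncentral t | Power for 31 m in smaller sex, normal / t |
|---|---|---|---|
| 50:50 | 31.1 / 31.1 m | 31.6 / 31.6 m | 80% / 79% |
| 40:60 | 34.8 / 28.4 m | 35.6 / 28.7 m | 70% / 69% |
| 30:70 | 40.2 / 26.3 m | 41.6 / 26.5 m | 58% / 55% |
| 25:75 | 44.0 / 25.4 m | 46.1 / 25.5 m | 51% / 47% |

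On the normal approximation, power for 31 m stays at or above 75% in both sexes from about 44.5% to 55.5% men, and at or above 70% from about 40% to 60%.

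**Which sex would be smaller?** The documents do not settle this. The Abstract's female predominance points to fewer men; the post-menopausal criterion removes some women and points the other way. The remaining exclusions say little. "History of invasive breast cancer" and the osteoporosis criterion are not restricted to women as written, and sections 4.4 and 9.4 count testosterone among the excluded hormone therapies.

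**What uses the 31 m?** The sample size rests on the 22 m comparison. The primary model adjusts for sex but does not estimate the effect by sex. None of the aims in section 2.2 is specific to one sex. No planned analysis draws on the figure.

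**The case for a change.** The best case for a change is that the protocol chose to publish a power claim by sex, and such a claim should carry its condition. The cost is one sentence, and the trial's biology makes readers likely to look at men and women separately. At 30% men there would be about 23 evaluable men across both arms (75.6 × 0.3 = 22.7), with 55% to 58% power for 31 m. A reader relying on section 7.4 would expect more.

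Much of this stands. The equal-split assumption is real, unstated and not enforced by stratification, and stating it would be good practice.

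It does not show the sentence to be wrong. Planning assumptions are seldom secured by design; the 10% loss to follow-up is not secured either. Section 7.4 claims sufficient power without naming a level, so the 80% benchmark is an inference, though the √2 match makes it the likeliest reading. If a lower level was meant, the claim survives a moderately unequal split. The 30% and 25% rows have no anchor in the documents. Anyone who later looks at the sexes separately will have the actual numbers and confidence intervals, which would replace the planning figure.

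**Conclusion.** No change is needed. The 31 m is correct arithmetic for half the sample, and the assumption behind it can be recovered in one line from the two published figures. What is missing is a supporting detail: about equal numbers of men and women (47% to 53% men after rounding), a common SD, equal loss to follow-up, and the 80% power stated for 22 m.

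If the split departs from this, the smaller sex falls short: by about 4 to 5 m at 40:60 (34.8 to 35.6 m against 31 m) and by about 9 to 11 m at 30:70 (40.2 to 41.6 m). The larger sex then does better than stated. The documents establish neither that such a split will occur nor its direction. The 22 m comparison, the 84 subjects, the primary analysis and every planned secondary analysis stay the same whether or not the assumption is written down. The judgement would differ if the plan contained a test within sex or an interaction test that relied on the 31 m; it contains none.

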7.5 Interim monitoring guidelines

We have not planned for formal interim analyses for efficacy and therefore there are no stopping rules for efficacy for this trial. This is a Phase II trial which will be useful in supporting future studies of the intervention even if null. This project will have a DSMB who may of course consider whether to stop the trial or not if there is an increased risk of adverse events or toxicity.

7.6 Protocol violations

Serious protocol violations such as discontinuation of experimental treatment unrelated to AEs will be carefully recorded and regularly reviewed by the Principal Investigator at each site and by the lead site. Remedial changes in procedure will be recommended where feasible to reduce the incidence of such violations. The causes and circumstances of all violations will be documented where known for purposes of future secondary analyses and interpretation. Because all primary analyses will be intent-to-treat, it is

essential that violations be kept to a minimum especially where it is possible to influence their rate of occurrence.

7.7 Safety and masking analysis

All subjects will be assessed for toxicity and included in the safety analysis. This analysis will include summaries of the incidence and grade of toxicities. Safety interim analyses will be performed and reported to the DSMB. Subjects will be evaluated for SAEs.

Chapter 8. Quality Control

Design strategies and monitoring activities throughout the study will ensure the integrity and high quality of the data. Design strategies include randomization of treatment assignment, masking, and training and certification of personnel. The rigorous monitoring program includes data queries and performance monitoring over the time of the trial.

8.1 Personnel training

Prior to randomization of the first subject in the study protocol, each site PI will ensure that staff has completed appropriate training and that all documentation including sIRB approval (and local IRB approvals, if required) is completed and available. The purpose of training is to ensure that study personnel are carrying out the protocol in a consistent way and are adhering to good clinical practice guidelines. Staff will have current Human Subjects Training Certification on file. Before enrollment begins, study coordinators and research assistants who will perform the outcome assessments will be trained in all procedures, including completion of case-report forms (CRFs).

The PI and research staff will constitute the first line of monitoring of the safety of the human participants. Surveillance for AEs will consist of questioning subjects about potential AEs at every study contact, having subjects report any adverse event to the study team, and having subjects undergo vital sign checks and physical exams during each study visit. Laboratories will be performed to ensure safety of initiating study drug and ten only as clinically indicated.

All study personnel are required to read the consent form, the protocol and the manual of procedures (MOP).

8.2 Data quality

The site PI will perform continuous monitoring of data quality and completion of CRFs. The data coordinating center (DCC) will create computer modules to identify discrepancies and incomplete data. These reports are tracked until each problem is resolved and corrected in the database.

Periodic audits of each enrollment site will be conducted by the lead site. The monitoring staff will review database forms and source documents to ensure that the information on the forms is complete and consistent with the source documents. All consent forms be audited.

Chapter 9. Participant Safety and Confidentiality

9.1 Consent

Written consent will be obtained for enrollment from participants. For each consent process, study personnel will discuss the details of the study, the risks and benefits, and the subject's rights and responsibilities if they choose to participate in the trial and their right to refuse to participate. It will be made clear that their clinical care will not be affected by their decision. Subjects will be permitted to provide verbal consent over the phone prior to being scheduled for a screening visit. A consent script will be provided and documentation of verbal consent will be noted. Written consent will be obtained at the screening visit or before.

9.2 Institutional Review Board process

The CCC and Field Centers will rely on a single IRB (sIRB) of record (University of Pennsylvania's IRB) and obtain approval and reliance agreements. When sIRB approval is obtained, site specific ICFs will be sent to the DCC along with the notice of approval. These materials must be on file in the DCC before a center can begin enrolling participants into the clinical trial.

9.3 Laboratory values

The following clinical laboratory tests will be measured at screening (or baseline).

9.3.1 Hematology

Complete blood count with differential, including hemoglobin, hematocrit, and platelets.

9.3.2 Chemistry

Basic metabolic panel including blood urea nitrogen, creatinine, and calcium.

